6.3 Biopsy Collection Visit

The Biopsy Collection visit will occur on the same day as the abdominoplasty surgery. The following procedures will be performed prior to and during abdominoplasty surgery:

1. Review of subject medical history.
2. Assess and record any additions, changes and/or deletions in prescription and nonprescription concomitant medications since the previous study visit.
3. Record severity and duration of any adverse device effects following RF treatment and assess for any new adverse device effects.
4. Biopsy collection procedure:
 - a. Refer to the patient chart and identify the RF treatment location.
 - b. During the biopsy collection procedure, at least one skin biopsy (approximately 10 mm x 10 mm; full thickness) will be taken from the area treated with RF; and at least one skin biopsy (approximately 10 mm x 10 mm; full thickness) will be taken from an equivalent contralateral non-treated area as a control.

c. Each biopsy sample will be immediately placed in the prepared fixative vials, making sure the samples are fully submerged in the solution. The vials will be labeled with the subject ID number, subject initials and biopsy date. The vials will be randomly numbered, and the numbers of the vials containing the biopsy from the RF treated and control skin will be recorded in the patient chart. The histologist will remain blinded to the nature of each biopsy sample (treatment or control).

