4 STUDY DESIGN

This is a single-center, prospective, non-randomized, open-labeled study in approximately 14 subjects, age 24 to 60 years, who are scheduled for abdominoplasty, and will undergo one RF treatment in the abdominal region. Subjects will receive 1 RF treatment with the truSculpt device [REDACTED]

[REDACTED]

One treatment will be performed by the truSculpt device on one abdominal subarea, while the other abdominal subarea will not be treated and will serve as a control. Subjects will have incisional or full-thickness punch skin biopsies. Biopsies will be harvested from tissue to be removed during the abdominoplasty, and will subsequently be cultured. At least two biopsy samples for each subject will be obtained during the abdominoplasty: at least one from the treatment area and at least one from the control area. The purpose of the biopsies is to examine and compare potential histological changes in cutaneous and sub-cutaneous tissue levels that occur as a result of RF treatment.

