5.2 Subject Numbering

Each enrolled subject will be assigned a subject ID number, comprised of the sequential number assigned for each subject treated and the subject initials. The subject initials will be comprised of the first letter of the first and last name.

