9 DATA ANALYSIS PLAN

9.1 Sample Size

The planned sample size of up to approximately 14 subjects was determined based on clinical judgement to provide sufficient information to evaluate the performance of RF treatment for lipolysis of abdominal fat.

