11.6 Data Collection, Record Keeping and Storage

The principal investigator is responsible for assuring that all study records including case report forms (CRFs), informed consent forms, device accountability records, source documents (e.g., medical records, histology reports etc.) and other study records are complete, accurate and recorded in a timely manner.

CRFs should not be the only record of a patient's participation in the study and will be used for transcribing data from source documents which are the point of first entry of data collected for each subject (with the exception of documents listed under **B**). The investigator or research staff at the site will ensure that:

A. Source documentation thoroughly and adequately documents:

1. That patient is participating in a clinical study and has been properly informed and consented prior to participation in the study,
2. Medical history,
3. Concomitant medications,
4. Patient's condition upon entering and during the course of the study,
5. Any adverse event(s) that might have occurred (in addition to the Visit CRFs and/or Adverse Device Effect CRF and/or Cutera SADE form completed),
6. Results of any diagnostic tests/histology conducted during the study.

B. The following data will be recorded directly onto CRFs:

7. Patient meets study inclusion and exclusion criteria,
8. A record of the treatment parameters, including the date of each RF treatment and any other adjunct therapy, a drawing of the patients abdomen showing the treatment location, and the vial numbers containing control and treatment biopsies,
9. Any protocol deviations,
10. Subject Questionnaire(s),
11. Study related improvement assessments by the investigator or investigator's designee,

12. Treatment-related pain ratings.

C. The following documents will be maintained in the study records:

13. The Investigator or the research staff will check signed informed consent for accuracy and will always keep the original copy of the signed informed consent in the CRF binder.
14. All correspondence with an Institutional Review Board (IRB), the sponsor, or FDA including required reports will also be retained in the study records.
15. Records of receipt, use or disposition of the investigational device.

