11.7 Subject Confidentiality

This study preserves the confidentiality of all subjects under the Health Insurance Portability and Accountability Act of 1996 (HIPAA) Privacy Rule. The following safeguards will be in place to protect the privacy of the individuals who are the subjects of the health information to be used in the research and the confidentiality of that information:

The subjects will be informed by the investigator or the investigator's designee that their medical records will be kept as confidential as possible but may be subject to review by: (1) Cutera, or its representative; (2) reviewing IRB; and/or (3) by appropriate regulatory bodies (e.g. the US Food and Drug Administration (FDA), Department of Health and Human Services (DHHS) agencies).

Only pieces of personal information required for purposes of the study will be collected. The personal information will be collected and used to ensure subject eligibility for study participation, to conduct the study and to assess the results of the study as required and permitted by law. Subjects have the right to see and copy any of the information gathered about them and request changes if the information is not correct, until it is no longer kept by the investigator. Permission to use or disclose personal information, except for that has been collected and relied on may be cancelled by the subject by written notice. If the subject is withdrawn from the study, the information collected to that time may still be used to preserve the scientific integrity of the study. There is no expiration date to this authorization.

Subjects' identities will be kept confidential. Subjects will be assigned a unique study code that will not reveal the subjects' identity, and this code will be used on all study documents. To protect subject identity with regards to the photographs taken of the treatment areas, care will be taken to cover areas of photographs to protect identity. Techniques such as covering of eyes on full face photographs,

cropping off portions of the face in close-up photos will be used to obscure identifying characteristics in photographs. The results of research, including photographs, may be published in scientific journals, presented at medical meetings, and used in training and marketing materials but subject identities will not be disclosed.

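### The vial labels let a histologist who sees them group one subject's treated and control samples, and the plan describes no step that hides the identifiers before reading

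*Combined protocol and SAP*

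**What the plan says.** Section 6.3, step 4c treats each vial in two ways. On identification it says: "The vials will be labeled with the subject ID number, subject initials and biopsy date". On masking it says: "The vials will be randomly numbered, and the numbers of the vials containing the biopsy from the RF treated and control skin will be recorded"; the place of record is the subject's chart. It then states the aim: "The histologist will remain blinded to the nature of each biopsy sample (treatment or control").

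Section 11.6 also places the key on the case report form, listing "the vial numbers containing control and treatment biopsies" among the items entered there directly.

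Section 4 fixes the minimum number of samples per subject: "at least one from the treatment area and at least one from the control area". Section 6.3, step 4b repeats this minimum and takes the control from the matching untreated site on the other side.

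The read supports the primary endpoint in section 4.1.1.1, which is fat necrosis with the skin layers spared, compared with untreated tissue. Section 4 describes the study as open-label and single-center. Section 9.3.1 plans a descriptive summary and no hypothesis test.

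No section states what appears on the material the histologist reads, in what order samples are read, or whether each is scored alone or beside its partner.

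**The concern.** Random numbering hides treatment status well when nothing else connects the specimens. Here three other label items are identical for all vials from one subject, so a reader who sees them can reassemble the subject's set. The design also tells that reader that every set contains both kinds of tissue. A reader who believes one sample shows necrosis then has a reason to expect the other to look normal, and the two reads stop being independent.

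This matters because treatment is open-label and the masked read is the only protection described for the primary endpoint. The plan gives no grading scale, threshold or definition of a positive sample, so the reader's judgement is the measurement. With no formal test, the descriptive contrast between treated and control areas is the whole efficacy result. The endpoint also combines two tissue levels in full-thickness samples. A cue in the skin layers may suggest which of two linked samples was treated and colour the reading of the fat, or the reverse.

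**Working it through.** The plan gives no figure on this point. Section 9.1 says "The planned sample size of up to approximately 14 subjects was determined based on clinical judgement", and there is no alpha, power or effect size to reproduce. The steps below describe the mechanism and do not estimate bias.

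**1. Does the label link samples?** Subject ID, initials and biopsy date are common to all vials from one subject, because all are taken on the day of surgery. Under section 5.2 the ID is "comprised of the sequential number assigned for each subject treated and the subject initials". Samples can therefore be grouped by subject. No label item encodes side or treatment.

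**2. How much uncertainty remains?** Assume 14 subjects with exactly one treated and one control vial each, so 14 × 2 = 28 vials.
- Unlinked: C(28,14) = 40,116,600 possible assignments.
- Linked: 2^14 = 16,384 possible assignments.

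Linking removes much of the uncertainty, but the random numbers still leave the side within every pair unknown.

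**3. What does knowing one vial say about another?** For a subject with t treated and c control vials, a vial known to be treated makes another vial from that subject control with probability c/(t + c − 1). A vial known to be control makes another treated with probability t/(t + c − 1).

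| Layout (treated + control) | Known treated: other is control | Known control: other is treated |
|---|---|---|
| 1 + 1 | 100% | 100% |
| 2 + 1 | 50% | 100% |
| 1 + 2 | 100% | 50% |
| 2 + 2 | 66.7% | 66.7% |

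For unlinked vials the comparable figure is 14/27 = 51.9%. The partner is fixed for certain, whichever vial is known, only in the 1 + 1 layout. Even there, "known" means that the first call is correct.

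**4. How much does linkage help a reader guess status?** Assume an equal-variance normal signal-detection model in which d′ is the visible separation between treated and control tissue. The chance of a correct guess is Φ(d′/2) for a vial judged alone and Φ(d′/√2) for a linked 1 + 1 pair. The d′ values are assumptions.

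| Assumed d′ | Single vial | Linked pair |
|---|---|---|
| 0 | 50.0% | 50.0% |
| 0.5 | 59.9% | 63.8% |
| 1 | 69.1% | 76.0% |
| 2 | 84.1% | 92.1% |
| 3 | 93.3% | 98.3% |

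With no visible difference, linkage gives nothing. Where tissue cues exist, it sharpens them, by about 7 percentage points at d′ = 1 (76.0 − 69.1 = 6.9) and 8 at d′ = 2 (92.1 − 84.1 = 8.0). These are probabilities of guessing status. They are not the size of any bias in the endpoint.

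**The case against.** The strongest reply is that the labels do not contradict the blinding that is promised. Section 6.3 blinds the histologist to treated or control status, and does not claim blinding to subject or pairing. The key sits in the chart and on the case report form. This is correct. A reader of the plan might infer that the labels unmask the samples, or that the random numbers protect little. The documents support neither reading: a call on one sample is the reader's inference, not disclosure of the key, and without a tissue cue a guess stays at 50%.

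It also stands that the histologist's sight of the label is an inference. Step 4c describes labelling at collection and is silent about what reaches the microscope. It neither states the exposure nor prevents it.

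A further objection is that linkage need not exaggerate the result. If treatment had no visible effect, a forced choice would fall on the treated sample half the time, and the expected contrast would be zero. If necrosis were obvious, an unlinked reader would recognise it too. This limits the claim to amplification of cues already present.

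Finally, masked paired reading is a legitimate way to compare tissue within a subject, which is what section 4 sets out to do. That also stands. But the plan does not say that it chose paired reading, and the choice should be stated.

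**Conclusion.** The concern holds as a moderate, avoidable weakness in masking. It rests on one inference (that the histologist can see the identifiers) and one fact (that the plan describes no step to prevent this). If the inference is right, reads within a subject are not independent, and an apparent contrast on an unscaled, subjective endpoint can be amplified. The effect is largest with one vial per side, and it needs some visible cue to work on.

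No sample size, error rate or other figure in the plan is affected. A reader might infer a count of compromised controls, for example 7 to 14 of 14 if 50% to 100% of treated samples showed a change (0.5 × 14 = 7; 1.0 × 14 = 14). The documents do not support such a count. It needs an assumed rate of visible change, exactly one vial per side, correct first calls, every treated sample read before its control, and a reader who deduces the second result without examining the sample. If order were random and scores fixed at first reading, about half the controls would follow their partner (3.5 to 7), which shows how far the figure depends on unstated conditions.

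A separate, minor privacy point: section 11.7 says "Subjects will be assigned a unique study code that will not reveal" identity, while section 5.2 builds the ID from initials and step 4c prints them on the vial. The masking argument does not depend on it.

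**What to change.** Amend section 6.3, step 4c in three respects.

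1. Material reaching the histologist carries the random number only. Subject ID, initials and date stay with the key already recorded in the chart and on the case report form. If the collection vial needs those items for custody, mask them or recode the specimen before reading.
2. Samples from different subjects are mixed and read in random order.
3. Each sample is scored alone and its score locked before any side-by-side comparison. If such a comparison is wanted, it remains masked and is reported as a second step.

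No visit, procedure or subject number changes. The costs are that traceability depends on the key, and that specimens must be recoded or held for batch reading. Batching is more than a relabelling exercise. The Protocol Summary plans subjects from June 2017 to June 2018, and two samples arriving together from one center could be paired without any label. The change has to be in place before reading starts, because masking cannot be restored afterwards.

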7 FADVERSE DEVICE EFFECTS

7.1 Definitions

7.1.1 Adverse Device Effect (ADE)

An adverse device effect (ADE) is defined as any untoward medical occurrence, unintended disease or injury, or untoward clinical signs (including abnormal laboratory findings) in subjects, device users or other persons, related to the investigational medical device. ADEs may be previously identified in nature, incidence, severity or outcome in the study protocol, informed consent document, device operator manual, other risk analysis documentation or regulatory application.

7.1.2 Serious Adverse Device Effect (SADE)

A serious adverse device effect (SADE) is any adverse device effect, related to the use of an investigational device or clinical study device, that:

- led to a death;
- led to a serious deterioration in the health of the subject that:
 - resulted in a life-threatening illness or injury;
 - resulted in a permanent impairment of a body structure or body function;
 - required in-patient hospitalization or prolongation of existing hospitalization;
 - resulted in medical or surgical intervention to prevent permanent impairment to a body structure or a body function
- led to fetal distress, fetal death or a congenital abnormality or birth defect.

7.1.3 Anticipated Serious Adverse Device Effect (ASADE)

[figure not shown]
An anticipated serious adverse device effect (ASADE) is any SADE on health or safety or any life-threatening problem or death caused by, or associated with the device, if that effect, problem, or death was previously identified in nature, severity, or degree of incidence in the investigational plan, informed consent, operator manual, other risk analysis documentation or regulatory application; or any other serious problem associated with a device that relates to the rights, safety, or welfare of subjects.

7.1.4 Unanticipated Serious Adverse Device Effect (USADE/UADE)

An unanticipated serious adverse device effect (USADE) is any SADE on health or safety or any life-threatening problem or death caused by, or associated with the device, if that effect, problem, or death was not previously identified in nature, severity, or degree of incidence in the investigational plan, informed consent, operator manual, other risk analysis documentation, or regulatory application; or any other unanticipated serious problem associated with a device that relates to the rights, safety, or welfare of subjects.

In subjects, the ADEs/SADEs include the effects related to the investigational medical device (clinical study device), the comparator or the procedures involved. For device users or other persons (other clinical staff in the treatment room) ADE/SADE is restricted to the effects related to investigational medical devices. ADEs/SADEs may include the effects (1) resulting from insufficient or inadequate instructions for use, deployment, installation, or operation, or any malfunction of the investigational medical device; or (2) resulting from user error or from intentional misuse of the investigational medical device.

Figure 1. Flowchart for classification of adverse device effects [19]

7.2 Recording Adverse Device Effects

All potential ADEs will be evaluated and must be recorded in the subject's medical chart and in the study case report forms. ADEs will be monitored and tracked from the time of the first RF treatment.

At each contact with the subject, the Investigator will seek information on ADEs by specific questioning and, as appropriate, by examination. ADEs may be observed by the Investigator and/or clinical research staff, elicited from the subject and/or family member or volunteered by the subject. All observed and volunteered adverse signs and symptoms (both expected and unexpected), regardless of severity or frequency, will be recorded in the case histories (medical chart and CRFs). Included in the description should be the nature of the sign or symptom, the date of onset, date of resolution (duration), the severity, whether the event was expected or unexpected (anticipated or unanticipated), the relationship to study treatment or other therapy, the action taken (if any), and the outcome.

All SADEs and UADEs must be reported according to Cutera and IRB requirements.

7.3 Follow-up of Subjects after ADEs

All reported ADEs should be followed until resolution or until the subject's participation in the study ends. Resolutions of such events are to be documented on the appropriate CRF pages. All ADEs that result in permanent discontinuation from this clinical trial, whether serious or not, will also be reported on the Subject Non-Completion of Study Form.

8 POTENTIAL RISKS / BENEFITS

8.1 Potential Risks

The known risks and adverse device effects associated with the study device or treatment procedure are shown in Table 3.

Table 3. Potential Study Risks

Table 3. Potential Study Risks or ADEs/SADEs			
STUDY DEVICE/PROCEDURE RELATED			
Type of Adverse Device Effect	Severity	Expected Duration	Frequency
Abrasion	Mild to Severe	3-14 days	Very Rare
Bleeding	Mild	Up to 1 hour	Very Rare
Blanching	Mild	> 24 hours	Very Rare
Blistering	Mild to Severe	1-14 days	Rare
Burn	Moderate	1-3 weeks	Rare
Contour Abnormalities/Cutaneous Depressions	Mild to Severe	> 1 month	Uncommon

Crusting/Scabbing	Mild to Severe	3-14 days	Rare
Edema (Swelling)	Mild to Moderate	< 72 hours	Very Common
Erythema (Redness)	Mild to Moderate	< 24 hours	Very Common
Hyperpigmentation	Mild to Severe	> 1 month	Rare
Hypopigmentation	Mild to Severe	> 1 month	Very Rare
Infection	Mild to Severe	2-14 days	Rare
Palpable nodules	Mild to Moderate	> 1 month	Common
Oozing	Mild to Severe	2-14 days	Very Rare
Pain (Discomfort)	Mild to Severe	During procedure	Very Common
Purpura (Bruising)	Mild to Moderate	7-21 days	Common
Scarring	Mild to Severe	> 1 month	Rare
Textural Changes	Mild to Severe	> 1 month	Rare
Partial, over treatment, and/or no treatment with the study device(s) due to equipment problem (device malfunction)	Mild to Severe		Rare
Improper treatment (partial, over-treatment, and/or no treatment) with the study device(s) due to user error	Mild to Severe		Rare
Unintended injury to subject, user or others due to user error (e.g., unintentional treatment to non-target location)	Mild to Severe		Rare

8.2 Potential Benefits

The subjects may or may not benefit from the treatment. Potential benefits include improved appearance of the treated abdominal and flank region and circumferential reduction in the treated abdominal and flank region. There is no guarantee of success.

8.3 Risk Management

The Investigator chosen for this study will have extensive and safe experience with the use of RF systems in dermatology applications. This is the most critical element in managing subject risk. In addition, the Investigators will be trained on the use of the Cutera RF device and any investigational handpieces.

9 DATA ANALYSIS PLAN

9.1 Sample Size

The planned sample size of up to approximately 14 subjects was determined based on clinical judgement to provide sufficient information to evaluate the performance of RF treatment for lipolysis of abdominal fat.

9.2 Analysis Sets

The efficacy analysis set will include all enrolled subjects who complete the RF treatment session using the study device.

The safety analysis set will include all subjects enrolled in the study who start the RF treatment session using the study device.

Missing data will not be imputed for efficacy or safety endpoints.

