4.1 Study Endpoints

4.1.1 Efficacy endpoints

4.1.1.1 Primary Efficacy Endpoint

- Histological evaluation of tissue for selective fat necrosis, with sparing of the dermis and epidermis, following truSculpt treatment vs. untreated bilateral control.

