6.2 RF Treatment Visit

The following procedures will be performed at the RF Treatment Visit:

1. If needed, cleanse subject's treatment area with a mild cleanser to remove any cosmetics, perfume or lotions and then dry the area.
2. Prior to performing RF treatment, the Investigator should confirm the subject continues to meet the study eligibility criteria, including asking about any changes in medical history and/or concomitant medications or significant increase or decrease in subject weight.
3. Using a surgical marker, mark the subject's abdomen as it will be marked on the day of the subsequent planned abdominoplasty procedure.

4. Place the return pad on the subject's upper lateral back. Connect the neutral electrode cable after the return pad has been applied.
5. The subject should be lying down and comfortable while undergoing RF treatment and the operator should have easy access to the treatment area.
6. Conduct RF treatment according to the parameters listed in Table 2 with one imprint applied to the subject's abdomen over the tissue intended to be removed during the following abdominoplasty procedure.

Table 2. TruSculpt RF Device Treatment	
RF Power	[REDACTED]
Pulse Duration	[REDACTED]
Frequency	[REDACTED]
Target Skin Temperature	[REDACTED]
Handpiece Size	[REDACTED]

7. Place the handpiece on the skin of the area to be treated and ensure the electrode is in full contact with the skin at all times. Do not apply excess pressure as this may diminish treatment effects and cause additional subject discomfort. The operator must wear surgical gloves during RF treatment.
8. After the imprint is delivered, an image will be taken of the subject's markings and post-treatment hyperemia pattern showing the location of the imprint. The image will be added to the subject's chart. The pulse duration for the imprint and the target temperature achieved during RF treatment will be recorded in the subject's chart.
9. The subject will be asked to rate the average level of discomfort experienced during and after completion of treatment using the Pain Rating Scale found in Appendix 3.
10. Investigator will assess and record any immediate post-treatment adverse device effects.
11. The "Before and After Treatment Instructions" will be explained and provided to the subject (see Appendix 4).

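### The efficacy set in 9.2 takes only completers of the RF session, so a sparing failure in a subject whose session was stopped could be missing from the histology summary

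*Combined protocol and SAP*

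**What the plan says.** Section 9.2 (Analysis Sets) defines two sets by different events. For efficacy: "The efficacy analysis set will include all enrolled subjects who complete the RF treatment session using the study device". For safety: "The safety analysis set will include all subjects enrolled in the study who start the RF treatment session using the study device". It adds: "Missing data will not be imputed for efficacy or safety endpoints".

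The sole efficacy endpoint (4.1.1.1) is histological evaluation for "selective fat necrosis, with sparing of the dermis and epidermis, following truSculpt treatment", compared with untreated tissue. Section 9.3.1 plans no formal testing and summarises this endpoint descriptively for treated and control areas. It does not name its analysis set.

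On specimens, section 4 says: "At least two biopsy samples for each subject will be obtained during the abdominoplasty". Section 6.3 takes at least one full-thickness biopsy from the treated area and at least one that "will be taken from an equivalent contralateral non-treated area as a control". Neither section makes collection depend on a completed session.

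On treatment, 6.2 step 6 reads: "Conduct RF treatment according to the parameters listed in Table 2 with one imprint applied". Step 10 follows: "Investigator will assess and record any immediate post-treatment adverse device effects".

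**The concern.** By using completion for one set and start for the other, 9.2 itself allows for subjects who begin the session and do not finish it. Membership of the efficacy set is therefore decided after treatment has begun.

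For fat necrosis this is defensible, because incomplete exposure dilutes the effect. For sparing of the skin the argument is weaker. A session cut short because the skin reacted is one in which sparing may have failed, and dropping that subject can only move the sparing result in the favourable direction. Section 9.4 tabulates adverse effects, terminations due to them and pain ratings, but no histology, so nothing in the visible plan returns such a subject's biopsy to a summary.

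At stake is whether the histology summary of a small descriptive study shows a sparing failure that occurred in a treated subject.

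**Working it through.** **Figure to reproduce.** There is none. Section 9.1 sets up to approximately 14 subjects on clinical judgement, and the documents give no error rate, power, effect size or stopping rate.

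**Step 1: which subjects the two definitions separate.** This applies 9.2 to the cases that 6.2, Table 3 and 5.3 allow for:

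| Case | Safety set | Efficacy set | Consequence for the sparing summary |
|---|---|---|---|
| Completes; reaction first seen at the check in 6.2 step 10, or later | Yes | Yes | None |
| Completes; sparing failure seen only on histology | Yes | Yes | None |
| Stopped by malfunction or user error, no injury | Yes | No | No bias need follow |
| Stopped during the imprint for a skin reaction, biopsied | Yes | No | Histology exists but is left out |
| Stopped for a skin reaction, then discontinued under 5.3 with no specimen | Yes | No | No histology to recover |

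Only the fourth row gives the problem.

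**Step 2: which set the summary uses.** Section 9.3.1 names none. It stands under the heading for efficacy endpoints (9.3), and 9.2 defines one efficacy set. Use of completers is the natural reading, but it is an inference.

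**Step 3: illustration of size.** Assumptions that are not in the plan: all 14 subjects start, sparing is scored yes or no, exactly one subject fails, and that subject was stopped and biopsied. The intervals are exact (Clopper-Pearson) 95%.

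- All starters: 1/14 = 7.1%. Lower limit 1 − 0.975^(1/14) = 0.0018, or 0.2%. The upper limit solves (1 − p)^14 + 14p(1 − p)^13 = 0.025, giving p = 0.339, or 33.9%.
- Completers only: 0/13 = 0%. Lower limit 0%. Upper limit 1 − 0.025^(1/13) = 1 − 0.753 = 0.247, or 24.7%.

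The intervals overlap widely. What changes is whether any failure is shown. If no such subject exists, the two summaries agree.

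**Step 4: the opposite direction.** Suppose instead that the one failure is in a completer, and the fourteenth subject was partly treated because of a malfunction and was spared. Completers then show 1/13 = 7.7% and all starters 1/14 = 7.1%. Widening the set can therefore also flatter sparing slightly, so neither set is sufficient alone.

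**Step 5: probability.** Table 3 lists blistering, burn and partial treatment only as Rare, with no percentage. No probability of a stopped session is estimated.

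**The case against.** The strongest reply is that the triggering event is hypothetical. Treatment is a single imprint, and no visible passage describes stopping it for a skin reaction. Table 3 attributes partial treatment to malfunction or user error, and it does not say that blistering or burn arises during the imprint. What counts as completing the session is undefined in the visible text, and the treatment description in section 4 and the settings in Table 2 are redacted. All of this stands.

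Second, a reaction strong enough to stop treatment would be recorded under 6.2 step 10 and 7.2 and counted in the safety set under 9.4. This also stands. What is lost is the histology, not the report of the injury.

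Third, section 4 is a general design statement. A reader might infer from it that a stopped subject is certain to be biopsied. The documents do not support that: 5.3 permits discontinuation after a serious reaction or in the subject's best interest, and a discontinued subject may have no specimen. Changing 9.2 would then recover no histology.

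Fourth, adding all starters also brings in subjects undertreated for technical reasons, who may be more easily spared, and using different sets for necrosis and sparing would break up a joint endpoint. Both objections stand, and they favour showing the whole endpoint in both sets.

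None of this removes the core point. As worded, the plan gives no place in the histology summary to the biopsy of a subject who started and did not complete.

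**Conclusion.** The point holds in a limited form. Section 9.2, read with 4.1.1.1 and 9.3.1, can leave the histology of a stopped but biopsied subject out of the summary, and if the stop was for a skin reaction the sparing result would look better than in all treated subjects.

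The conclusion rests on three assumptions: that 9.3.1 uses the efficacy set, that a stopped imprint counts as not completed, and that the specimen is taken. The size is unknown and may be zero. In the illustration it is the difference between showing one failure in 14 and none in 13.

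Two stronger readings are tempting. One is that subjects with skin injury are in general removed from the efficacy results. The text does not support this, because any reaction first seen after the imprint belongs to a completer. The other is that the study's conclusions or error rates are compromised. No test or decision rule is planned, so only a descriptive summary is affected. This is a cheap improvement, not a serious flaw.

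**What to change.** In 9.2 and 9.3.1:

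- Summarise the full histology endpoint, necrosis and sparing together, for all subjects who start the RF session and have available treated and control specimens, side by side with the completer set.
- State the number treated and the number evaluable.
- List each starter who did not complete the session or has no evaluable pair, with the reason and any recorded skin adverse device effect.

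The cost is a few sentences, one extra summary column and one short listing. No subjects, visits or procedures are added, since biopsies come from tissue already due for removal.

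The downside is that partially treated subjects may dilute the necrosis result and may also be more easily spared. Showing both sets, with the reason for each incomplete session, lets the reader judge this.
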